10.2.3. RBC Transfusions

Concurrent treatment for anemia with blood transfusions is allowed, at the discretion of the investigator, for low hemoglobin levels, symptoms associated with anemia (e.g., hemodynamic or pulmonary compromise requiring treatment) or comorbidity.

For any RBC transfusions (NTD or TD patients) received during the study, collect hemoglobin values just prior to transfusion.

Each TD patient will have a defined “pre-transfusion hemoglobin threshold” which will be calculated based on transfusion history and will be used for determining when to transfuse during the study. The baseline pre-transfusion hemoglobin threshold will be the mean of all documented pre-transfusion hemoglobin values during the 12 weeks prior to C1D1 of base study A536-04 (for patients without treatment interruption) or study A536-06 (for patients with treatment interruption). During treatment, if the pre-transfusion hemoglobin level is increased by ≥ 1 g/dL compared to the baseline pre-transfusion hemoglobin threshold for that patient, transfusion should be delayed by a minimum of 7 days and/or the number of units transfused should be reduced by 1 or more RBC units. Patients may be transfused at the investigator’s discretion for symptoms related to anemia or other requirements (e.g., infection). Patients may be transfused on the same day as ACE-536 is administered except on C1D1 for patients with treatment interruptions.

10.3. Treatment Compliance

ACE-536 will be administered as a SC injection at the clinical site by the study staff and will be documented in the study record. Monitoring for patient compliance with the treatment regimen is therefore unnecessary.

10.4. Randomization

This study does not require randomization and is open-label.

10.5. Treatments Administered

A patient without treatment interruption may continue to be dosed with ACE-536 at the same dose level (rounded to nearest A536-06 starting dose level) administered at their last dose in study A536-04 (unless a dose reduction is required based upon patient dose modification rules from study A536-06). All patients with treatment interruption will be initially treated with ACE-536 at a starting dose level of 0.8 mg/kg which has been determined to be safe and well tolerated by the SRT based on data from study A536-04. Please refer to [Table 2, Examples of Possible Starting Dose with Dose Modifications \(Reductions and Titrations\)](#), for additional information regarding treatments administered.

10.6. Safety Evaluation

Safety will be evaluated by the SRT, which is comprised at minimum of the coordinating investigator, medical monitor, and an independent hematologist. The role of the SRT will be described in greater detail in the SRT Charter. The SRT will review safety data periodically throughout the trial, including AEs, SAEs, laboratory results (including hematology and chemistry), vital signs, and erythroid response data.

10.7. Starting Dose Levels

A patient without treatment interruption may continue to be dosed with ACE-536 at the same dose level (rounded to nearest A536-06 starting dose level) administered at their last dose in study A536-04 (unless a dose reduction is required based upon patient dose modification rules from study A536-06). All patients with treatment interruption will be initially treated with ACE-536 at a starting dose level of 0.8 mg/kg which has been determined to be safe and well tolerated by the Safety Review Team (SRT) based on data from study A536-04. Examples of possible starting dose levels with dose modifications (reductions and titrations) are below for reference.

Table 2: Examples of Possible Starting Dose with Dose Modifications (Reductions and Titrations)

3 rd Dose Reduction	2 nd Dose Reduction	1 st Dose Reduction	Starting Dose Level	1 st Dose Titration	2 nd Dose Titration
	0.2 mg/kg	0.4 mg/kg	0.6 mg/kg	0.8 mg/kg	1.0 mg/kg
0.2 mg/kg	0.4 mg/kg	0.6 mg/kg	0.8 mg/kg	1.0 mg/kg	1.25 mg/kg
0.4 mg/kg	0.6 mg/kg	0.8 mg/kg	1.0 mg/kg	1.25 mg/kg	
0.6 mg/kg	0.8 mg/kg	1.0 mg/kg	1.25 mg/kg		

- Starting dose level for TD and NTD patients to be determined based on data from study A536-04 (range: 0.2-1.25 mg/kg).
- Starting dose level for patients without treatment interruption will be last dose level (rounded to nearest A536-06 starting dose level) administered in study A536-04 (unless a dose reduction is required based upon patient dose modification rules from study A536-06).
- Patients may be titrated up and down dose levels as required per protocol to meet dose modification and titration rules.
- Patients who require more than 2 dose reductions due to an AE should be discontinued from treatment and complete the EOT and EOS visits.
- The maximum dose titration will not exceed the maximum dose level tested in base study A536-04.

10.8. Individual Dose Modification Rules

The following dose modification rules include both PD and safety parameters which may require a dose delay and/or a dose reduction. These rules should be assessed prior to every dosing visit for all patients. If a dose delay is required, the patient should have weekly visits to assess hematology results and AEs until the patient is eligible to receive the next dose of ACE-536.

Observation on Dosing Day	Action	ACE-536 Dose Modification
Hemoglobin \geq 13 g/dL	Hold dose and monitor patient weekly until hemoglobin $<$ 12 g/dL	Resume dosing once hemoglobin $<$ 12 g/dL at the same dose level
Hemoglobin increase \geq 2 g/dL from the previous dosing day (not attributable to RBC transfusion)	Continue dosing	Reduce the dose by 1 dose level
Non-hematologic AE \geq Grade 3, or hematologic AE \geq Grade 4, at least possibly related to study drug	Hold dose and monitor patient weekly until resolution of AE to \leq Grade 1 or baseline	Resume dosing upon resolution of the AE to \leq Grade 1 or baseline and reduce the dose by 1 dose level ^a
Grade 3 leukocytosis (WBC $>100,000/\mu\text{L}$)		Discontinue treatment

^a Patients who require more than 2 dose reductions due to an AE should be discontinued from treatment and complete the EOT, PTFU, LTFU, and EOS visits.

10.9. Individual Dose Titration

10.9.1. Individual Dose Titration for NTD Patients

For all NTD patients (with and without treatment interruption), the dose level will be assessed for titration at Day 1 of every cycle starting at C3D1 (e.g., C3D1, C4D1, C5D1, etc.). The dose level should be titrated individually for each patient not to exceed the maximum dose level evaluated in the base study A536-04 as follows:

- If hemoglobin increase from baseline is $<$ 1.5 g/dL throughout the previous two cycles at the same dose level, the dose level will be increased by 1 dose level (unless dose modification is required).
- If hemoglobin increase from baseline is \geq 1.5 g/dL but not sustained for at least two consecutive measurements during the previous two cycles at the same dose level, the dose level will be increased by 1 dose level (unless dose modification is required).
- If hemoglobin increase from baseline is \geq 1.5 g/dL for at least two consecutive measurements during the previous two cycles at the same dose level, the dose level will be unchanged (unless dose modification is required).

Baseline hemoglobin to assess titration will be the average of two or more measurements performed during the screening period for base study A536-04 (for patients without treatment interruption) or study A536-06 (for patients with treatment interruption). Hemoglobin measurements within 2 weeks following RBC transfusion will be excluded from both the calculation of the mean baseline hemoglobin and for evaluation of dose titration for a patient during treatment.

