9.2. Discussion of Study Design

The primary endpoint is evaluating the long-term safety and tolerability of ACE-536 administration in patients with β -thalassemia who completed participation in A536-04. To support this endpoint, this study includes safety measurements that are considered standard for studies with investigational medications.

An open-label study, conducted in a limited number of patients, with protocol-specified procedures for dose reduction is considered appropriate for a long-term safety study in this target patient population. Individualization of dose level, using dose titration rules based on hemoglobin response and dose reduction rules based on safety information will maximize the proportion of patients having an erythroid response while maintaining safety.

Secondary endpoints were selected to evaluate the impact of ACE-536 on efficacy and PD parameters, including effects on hematologic parameters and on complications of thalassemia.

The initial dose level of 0.8 mg/kg has been selected for patients with treatment interruption based upon data from the ongoing A536-04 study. Dose levels utilized in this study will not exceed maximum dose levels tested in study A536-04.

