10.9.2. Individual Dose Titration for TD Patients

For all TD patients (with and without treatment interruption), the dose level will be assessed for titration at Day 1 of every cycle starting at C3D1 (e.g., C3D1, C4D1, C5D1, etc.). The dose

level should be titrated individually for each patient not to exceed the maximum dose level evaluated in the base study A536-04 as follows:

- If patient is transfused with ≥ 3 units during the previous 2 cycles at the same dose level, the dose level will be increased by 1 dose level (unless a dose modification is required).

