10.10. Other Considerations for Dose Modification, Delay or Discontinuation

For individual patients judged by the investigator to be at an unacceptable risk, but who do not meet the protocol-defined conditions for a dose modification or interruption, the investigator should consult with the medical monitor to decide whether to continue dosing at the same dose level, reduce the dose level, delay the patient's dose, or discontinue the patient's treatment with ACE-536.

Patient treatment interruption for site administrative reasons will be allowed between Cycle 17 and 18 and between Cycle 35 and 36 upon discussion with the sponsor.

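### A dose cut for a related severe adverse event is by default raised back to the level at which the event occurred if the patient then responds inadequately over two cycles (Protocol 10.8 and 10.9)

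*Protocol*

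**What the plan says.** **Reduction.** Under Protocol 10.8, a non-hematologic AE of Grade 3 or higher, or a hematologic AE of Grade 4 or higher, that is at least possibly related leads to a hold. Dosing restarts when the event has settled to Grade 1 or below "or baseline and reduce the dose by 1 dose level". Footnote a sets a limit: "Patients who require more than 2 dose reductions due to an AE should be discontinued from treatment".

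**Titration.** Protocol 10.9 covers all patients, at Day 1 of each cycle from C3D1.

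- Non-transfusion-dependent (NTD), 10.9.1: the trigger is a hemoglobin rise that stays below 1.5 g/dL over two cycles, or reaches it without holding for two consecutive readings. The consequence is given as "at the same dose level, the dose level will be increased by 1 dose level (unless dose modification is required".
- Transfusion-dependent (TD), 10.9.2: the trigger is 3 or more "units during the previous 2 cycles at the same dose level, the dose level will be increased by 1 dose level", with the same kind of exception.

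**Limits on going up.** The ceiling is the highest dose evaluated in A536-04. Protocol 10.7 adds: "Patients may be titrated up and down dose levels as required per protocol to meet dose modification and titration rules". None of these sections treats a patient reduced for an AE differently.

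**Rationale.** Protocol 9.2 says that individual titration together with "dose reduction rules based on safety information will maximize the proportion of patients having an erythroid response while maintaining safety".

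**The concern.** The two sets of rules pull against each other. Section 10.8 takes a patient off a dose level because of a related severe event. Section 10.9 can return the same patient to that level on hemoglobin or transfusion data alone. A lower dose may well give a weaker response, so the patients reduced for toxicity are plausibly more likely to meet the trigger.

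The increase is worded as what will happen, not as an option to consider. The site has to act to prevent it. The primary objective is long-term safety and tolerability, and 9.2 relies on the reduction rules to keep patients safe, so the default runs the wrong way for these patients.

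**Working it through.** No sample size, power or alpha figure is involved. The check follows the rules as written.

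**1. Does the exception in 10.9 stop the increase?** The exception applies when a dose modification is required. The 10.8 table works from what is observed on the dosing day and is assessed before every dosing visit. A patient with two cycles at the reduced level was allowed to restart because the AE had already resolved to Grade 1 or below, or to baseline. Unless something new has happened, no row of the table applies. The exception is silent and the increase stands.

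**2. Time to re-exposure.** Two cycles × 21 days = 42 days from the first reduced dose.

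**3. Worst-case sequence.** Take a start at 0.8 mg/kg, the starting level for patients with treatment interruption. Assume that each 0.8 dose is followed by a qualifying AE that resolves without delaying the next dose, and that the 10.9 trigger is met each time.

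| Cycle | Days from the first 0.8 dose | Dose (mg/kg) | What happens |
|---|---|---|---|
| 1 | 0 | 0.8 | First AE |
| 2 | 21 | 0.6 | First AE reduction |
| 3 | 42 | 0.6 | – |
| 4 | 63 | 0.8 | Raised under 10.9; second AE |
| 5 | 84 | 0.6 | Second AE reduction |
| 6 | 105 | 0.6 | – |
| 7 | 126 | 0.8 | Raised under 10.9; third AE |
| 8 | 147 | none | Third AE reduction required; footnote a stops treatment |

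The patient is re-exposed twice and has three qualifying AEs at one level. If the level at which the AE occurred were barred, three such AEs before stopping would have to occur at three falling levels (0.8, 0.6 and 0.4). If the 10.9 trigger is never met, the dose stays at 0.6 and there is no re-exposure.

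**4. How demanding is the TD trigger?** SAP 5.1 gives the protocol definition of TD as at least 4 units every 8 weeks. On the scale of two cycles, 4 × 6/8 = 3.0 units per 6 weeks. A TD patient at that minimum with no reduction in burden meets the trigger. Under the SAP programming rule of 11 units in 26 weeks, the minimum is 11 × 6/26 = 2.5 units per 6 weeks, just under it on average. Larger burdens can fall a good deal and still meet it:

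| Baseline, units per 8 weeks | Units per 6 weeks (× 6/8) | Largest reduction that still leaves 3 units: 1 − 3/(units per 6 weeks) |
|---|---|---|
| 4 | 3.0 | 0% |
| 6 | 4.5 | 33% |
| 8 | 6.0 | 50% |
| 10 | 7.5 | 60% |

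The trigger is a real condition, but a TD patient on a reduced dose can easily meet it.

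**The case against.** The other side has substance.

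- **Discretion exists.** Under Protocol 10.10, for a patient judged at unacceptable risk who meets no written modification condition, "the investigator should consult with the medical monitor to decide whether to continue dosing at the same dose level", reduce, delay or stop. That description fits a patient whose AE has resolved. Section 9.4 allows treatment to be stopped for an AE, and 12.2 requires AEs that might affect dosing to be reviewed before each dose.
- **Repeats are capped, and there is oversight.** Footnote a ends treatment when a third AE reduction is needed. The safety review team of 10.6, which includes an independent hematologist, sees AE and laboratory data periodically.
- **Movement both ways is intended.** Section 10.7 says so and 9.2 gives the reason.

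These points limit the harm without removing the default. Section 10.10 starts only when an investigator judges the risk unacceptable; a past AE reduction does not itself prompt the consultation. Footnote a limits how many re-exposures occur, not whether one occurs. Periodic review is not a check before a dose. The sponsor could say that the exception in 10.9 was meant to cover an earlier AE reduction, but the text does not say this, and 10.7 contains no such carve-out.

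A reader might also infer three stronger things that the documents do not support:

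- **That the dose goes back up automatically after two cycles.** It does not. The inadequate-response trigger must be met.
- **That the SAP would hide a recurrence.** SAP 5.2 lists all study data, 5.5 lists dosing details for each patient, and 5.8.1 lists all AEs with a separate listing of Grade 3 or higher. The sequence can be reconstructed. What is missing is a link in the summaries: the AE tables count a patient once per term, and 5.5 counts reductions and increases without their reason.
- **That the number of patients affected can be estimated.** The documents give neither a rate of AE-driven reductions nor the share who would then meet the trigger. Any frequency would only restate its assumptions.

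**Conclusion.** The point stands as a weak default in a written safety rule. A patient reduced for a related severe AE who then meets the inadequate-response trigger is, unless someone intervenes, returned to the level at which the AE occurred.

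Its size is re-exposure from 42 days after the first reduced dose and, at worst, three qualifying AEs at one level. That worst case assumes no hold time, an AE in the first cycle at that level each time, and a trigger met each time. Any hold for resolution lengthens the timeline. The number of patients affected is unknown and may be small among the up to 64 who may be eligible.

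The conclusion rests on reading the exception in 10.9 as referring to the dosing-day conditions of 10.8. It does not call the planned safety analyses into question. It is a cheap improvement to patient protection that is worth making.

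**What to change.** **Protocol 10.9.1 and 10.9.2.** Add to each: *A dose reduced for an AE under Section 10.8 is not increased back to the level at which the AE occurred unless the investigator and medical monitor agree and document the reason.* This uses the consultation already described in 10.10 and reverses the default. Re-escalation stays possible where the clinical case is good.

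**SAP 5.5 (optional).** Split dose reductions by reason (AE or hemoglobin rise), and flag patients whose dose was raised again after an AE reduction, with any recurrence. Protocol 14.5 already requires AE reports to record the action taken, including dose modification, so no new data are needed.

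**Cost.** A protocol amendment. Because it affects patient safety, Protocol 19 requires ethics committee approval and regulatory submission before it is implemented; nothing here suggests the immediate hazard that would justify acting sooner. The clinical price is that some patients may stay on a lower and less effective dose. The optional SAP change is one split and one flag or listing.

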10.9.2. Individual Dose Titration for TD Patients

For all TD patients (with and without treatment interruption), the dose level will be assessed for titration at Day 1 of every cycle starting at C3D1 (e.g., C3D1, C4D1, C5D1, etc.). The dose

level should be titrated individually for each patient not to exceed the maximum dose level evaluated in the base study A536-04 as follows:

- If patient is transfused with ≥ 3 units during the previous 2 cycles at the same dose level, the dose level will be increased by 1 dose level (unless a dose modification is required).

10.10. Other Considerations for Dose Modification, Delay or Discontinuation

For individual patients judged by the investigator to be at an unacceptable risk, but who do not meet the protocol-defined conditions for a dose modification or interruption, the investigator should consult with the medical monitor to decide whether to continue dosing at the same dose level, reduce the dose level, delay the patient's dose, or discontinue the patient's treatment with ACE-536.

Patient treatment interruption for site administrative reasons will be allowed between Cycle 17 and 18 and between Cycle 35 and 36 upon discussion with the sponsor.

11. STUDY PROCEDURES

Please refer to [Section 2](#), Schedule of Events for the schedule of procedures required for each visit.

11.1. Written Informed Consent

Patients will be required to sign an IEC approved ICF prior to any study related procedures, including screening evaluations.

11.2. Clinical Laboratory Tests

11.2.1. Local Laboratory Testing

The following laboratory assessments will be performed at the clinical site's local laboratory according to the laboratory collection recommendations. The sponsor may request additional safety tests be performed based on ongoing data review during the study.

- Hematology: RBC, nucleated red blood cells (nRBCs), white blood cell (WBC) with differential, hemoglobin, hematocrit, reticulocyte count, platelet count, mean corpuscular volume (MCV), mean corpuscular hemoglobin (MCH), mean corpuscular hemoglobin concentration (MCHC), and red blood cell distribution width (RDW).
- Serum chemistry: Sodium, potassium, AST, ALT, lactate dehydrogenase (LDH), total bilirubin, indirect bilirubin, alkaline phosphatase, blood urea nitrogen (BUN)/urea, creatinine, GGT, calcium, phosphorus, glucose, amylase, lipase, total protein, albumin, and uric acid.
- Urinalysis by dipstick analysis: pH, specific gravity, protein, glucose, ketones, blood, leukocyte esterase, and nitrite, with microscopic examination if indicated.
- Pregnancy test (urine or serum) and menstrual history for women of child bearing potential.
- Serum folate: required at screening for patients with treatment interruption to confirm eligibility; required at C1D1 and as required per schedule of events for all patients

11.2.2. Central Laboratory Testing

The following laboratory assessments will be performed at the central laboratory according to the laboratory collection recommendations. The sponsor may request additional safety tests be performed based on ongoing data review during the study.

- nRBCs
- EPO levels
- Peripheral blood smear
- Serum iron studies
- Urine chemistries include but are not limited to: microalbumin and creatinine

11.3. Other Safety Assessments

- Physical examination (including optional evaluation of gonadal size in males at specified timepoints)
- Vital signs: weight, heart rate, systolic and diastolic blood pressure.
- 12-lead ECG
- ADA testing: (Blood samples should be drawn and processed on-site for serum collection at the time points specified according to the relevant Laboratory Manual)
- The occurrence of a new malignancy or premalignant lesion will be monitored as an event of interest and should be included as part of the assessment of adverse events throughout the course of the study. Investigators are to report the development of any new malignancy or premalignant lesion as a serious adverse event, regardless of causal relationship to study drug, occurring at any time for the duration of the study, from the time of signing the ICF up to and including 3 years of follow up.

11.4. Pharmacokinetic and Pharmacodynamic Assessments

11.4.1. Pharmacokinetic Assessments

PK assessment of ACE-536 concentrations will be performed periodically as outlined in [Section 2](#), Schedule of Events. Blood samples should be drawn and processed on-site for serum collection at the time points specified. Additional details regarding PK collection and processing can be found in the relevant Laboratory Manual.

11.4.2. Pharmacodynamic Evaluations

PD assessments including hematologic laboratory assessments and transfusion information will be used to determine erythroid response to ACE-536. Please note specific timepoints according to the Schedule of Events ([Section 2](#)):

- An MRI will be performed at selected sites to evaluate LIC.
- An MRI will be performed to evaluate EMH masses (unless site does not have the feasibility to perform the assessment).
- A DXA will be performed at selected sites to evaluate total body, lumbar spine and total hip BMD.
- Patients with leg ulcers should have regular assessment of the leg ulcer(s) throughout the study. Photographs of the leg ulcer(s) pre- and post- dose should be provided when available to document any changes in the ulcer.
- A 6MWT will be performed at selected sites for NTD patients.
- Quality of Life tools including by not limited to the FACT-An and SF-36 questionnaires will be assessed.
- Biomarkers for iron metabolism may include serum iron, TIBC, transferrin, soluble transferrin receptor, calculated transferrin saturation, ferritin, and NTBI.

- Biomarkers related to the TGF β superfamily and/or iron metabolism, such as hepcidin, GDF15, GDF8, GDF11, Activin A and others may be tested in blood samples, to be determined.
- Hemoglobin electrophoresis samples will be collected for central analysis.
- The sponsor may perform additional sample analysis for biomarkers for exploratory research purposes only.

